[figure not shown]

## 1. LIST OF ABBREVIATIONS

Abbreviation	Explanation
ADR	Adverse Drug Reaction
AE	Adverse Event
ALT	Alanine Aminotransferase
AP	Arterial Pressure
APTT	Activated Partial Thromboplastin Time
AST	Aspartate Aminotransferase
BLQ	Below the Limit of Quantification
BMI	Body Mass Index
CI	Confidence Interval
CLcr	Creatinine Clearance
CRF	Case Report Form
CRO	Contract Research Organization
CS	Clinically Significant
ECG	Electrocardiogram
ESR	Erythrocyte Sedimentation Rate
FEV 1	Forced Expiratory Volume for a second
GCP	Good Clinical Practice
GGT	Gamma-glutamyltransferase
HBV, HCV	Hepatitis B and C
IC	Informed Consent
ICH	International Conference on Harmonization
ICH GCP	Guidelines for Good Clinical Practice of the International Conference on Harmonization
IEC	Independent Ethics Committee
ITT	Intent-to-treat
LME	Linear Mixed Effect Model
Mean	Mean value
N	Number of observations
PP	Per Protocol
PTT	Prothrombin Time
p-value	p-value for H 0 of test performed
SADR	Serious Adverse Drug Reaction
SAE	Serious Adverse Event
SAP	Statistical Analysis Plan
SD	Standard Deviation
SE	Standard Error
TESS	Treatment Emergency Sign and Symptom
VAS	Visual Analogue Scale
WHO	World Health Organization

## 2. INTRODUCTION

This document contains further details to the statistical analyses described in the protocol LDP0114 and is the primary source of all statistical analyses for the study.

### 2.1 STUDY DESIGN

The present study is a multicenter open-label randomized comparative Phase 3 clinical trial in parallel groups. The study will be conducted at 8 Russian sites. The total expected number of enrolled patients is 184 (92 per each group). Taking into account the possibility of 20% screen-failure rate, up to 230 patients will be screened.

[figure not shown]
The study will consist of 3 periods: screening and randomization, study therapy, follow-up.

Patients meeting all inclusion/exclusion criteria will be randomized into two groups (at a 1:1 ratio):

- Levopront® syrup 30 mg/5 ml — 10 ml t.i.d. for 7 days
- Libexin® 100 mg tablets — 1 tablet t.i.d. for 7 days

The study drugs will be taken 3 times a day (with the interval of not less than 6 hours, between meals) during 7 days. The first study drug administration will be performed at the clinical site on the day of randomization; the last study drug administration will be performed in the evening before Day 8.

Figure 2.1 Study diagram

**Table 2.1 Study procedure Schedule**

Visit (V)	Screening and randomization	Study treatment		Follow-up
	V1	V2	V3 ET or ED	TC
Day (D)	D1	D4	D8	D10
Visit window		± 1 day	± 1 day	± 1 day
Informed consent				
Patient's registration				
Demography data				
Medical history				
Physical examination				
Vital signs				
Body height and weight 				
Cough severity and frequency assessment with the "Six-point daytime and nighttime cough assessment scale"				
Cough intensity assessment with the visual-analogue scale.				
Laboratory testing:				
- hematology				
- biochemistry				
- urinalysis				
- pregnancy test 				
ECG				
Spirometry 				
Chest X-ray or fluorography 				
Inclusion/exclusion criteria				
Randomization 				
Study drug and Patient's dairy distribution to patient 				
Return and accountability of the study drug, Patient's dairy review				
Concomitant medications assessment				
AE assessment				

**Abbreviations:** ET — end of treatment, ED — early discontinuation, ECG — electrocardiography, AE — adverse events, TC – telephone contact

**Footnotes:**

 Pregnancy test will be performed at the clinical site using the test-strip (only for the women of childbearing potential including the women in menopause of less than two years) before chest x-ray of fluorography.

 At visit Day 1 pre- and post-bronchodilator spirometry will be performed. At visit Day 8 only pre-bronchodilator spirometry will be performed.

 Results of the chest x-ray or fluorography performed before signing the Informed Consent Forms a part of routine patient's examination for main disease (ARVI) can be used for the protocol purposes (if written conclusion report is available).

 Patient's randomization and distribution of the study drug to the patient (along with the Patient's dairy) on Day 1 will be performed only after assessment of all inclusion/exclusion criteria. The first dose of the study drug will be taken at the clinical site.

 The growth measure should be performed only during screening visit. For calculated values of lung function growth measured only at screening and weight measured during screening and Visit 3 (Day 8) should be used.

## 2.2 SAMPLE SIZE

The sample size is calculated for the primary efficacy endpoint - the proportion of

 Citation from the protocol

patients with response to therapy (daily cough symptoms permission to visit Day 8) and non-inferiority hypothesis.

According to available data in the literature (Schroeder K., Fahey T. Over-the-counter medications for acute cough in children and adults in ambulatory settings) in clinical studies antitussives difference between the active treatment group and the placebo group was about 44%. In the placebo-controlled study (Smith SM, Schroeder K., Fahey T. Over-the-counter (OTC) medications for acute cough in children and adults in community settings) the difference between the active treatment groups and the placebo group was 25% and 35%. According to the meta-analysis of clinical trials of levodropropizine in two placebo-controlled studies the difference between the efficacy of the study drug and placebo was 45% in the pediatric population of patients (study Fiocchi) and 39% in the adult population of patients (study Allegra, where efficacy of levodropropizine was about 80%).

According to ICH guideline, the selected non-inferiority margin (non-inferiority margin) should not exceed the minimum difference between the performance indicators of the active drug and placebo. Based on the above data, non-inferiority margin  $\delta = 20\%$  was chosen for the study.

The sample size estimation in the protocol amendment is based on the results of the study interim analysis that showed approximately 70% efficacy in both groups vs. 80% efficacy that had been projected initially. Thus, the interim analysis at  $\alpha = 0.05$  (one-sided) showed lack of power for the hypothesis testing ( $< 80\%$ ).

The sample size was calculated using the formula for non-inferiority for comparison of two independent proportions:

$$n = \left( Z_{\frac{\alpha}{2}} + Z_{\beta} \right)^2 \times [p_1 \times (100\% - p_1) + p_2 \times (100\% - p_2)] / (p_1 - p_2 - \delta)^2$$

where  $n$  – sample size for each group,  $p_1$  – success rate in the control group,  $p_2$  – success rate in the treatment group,  $\delta$  – non-inferiority margin,  $Z_{\frac{\alpha}{2}}$  is 1.645 for one-sided  $\alpha = 0.05$  and  $Z_{\beta}$  is 0.84 for 80% power.

In order to achieve power 80%, with corrected  $\alpha = 0.025$  (one-sided), expected efficacy rate of 70% in both groups, non-inferiority margin  $\delta = 20\%$ , and ED rate not exceeding 10%, 184 patients should be enrolled in the study at 1:1 ration (92 patients per treatment group).

Assuming the screen-failure rate of about 20%, up to 230 patients will be screened in the study.

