where n – sample size for each group, p_1 - success rate in the control group, p_2 – success rate in the treatment group, δ – non-inferiority margin, $Z_{\alpha/2}$ is 1.96 for one-sided $\alpha = 0.025$ and Z_{β} is 0.84 for 80% power. In order to achieve power 80%, with corrected $\alpha = 0.025$ (one-sided)^{20,21}, expected efficacy rate of 70% in both groups, non-inferiority margin $\delta = 20\%$, and ED rate not exceeding 10%, 184 patients should be enrolled in the study at 1:1 ration (92 patients per treatment group).

Assuming the screen-failure rate of about 20%, up to 230 patients will be screened in the study.

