### 7.2.3 Primary Efficacy Analysis

According to the Guideline EMA/EWP-482 (Superiority-non-inferiority and switching), in non-inferiority study primary analysis must be performed on Per-Protocol population (see chapter IV.1.4 Choice of analysis set of the guideline).

The main efficacy analysis population is defined as Per-Protocol (PP).

Study statistical testing hypothesis is expressed as:

H0: Lower bound of the 97.5% one-sided CI ( $p_1 - p_2$ )  $\leq -20\%$  => Non-inferiority rejected

H1: Lower bound of the 97.5% one-sided CI ( $p_1 - p_2$ )  $> -20\%$  => Non-inferiority accepted

The primary objective is to demonstrate the "non-inferiority" of Levopront® comparing to Libexin® with regards to the primary endpoint. For this purpose, the one-sided 97.5% Confidence Interval (CI) will be calculated for the two proportions difference — the rate of patients who responded to treatment (**cough absents**, when score is 0 or 1 at "six-point cough scale" vs. **cough presents**, when score is  $\geq 2$  at "six-point cough score") by Day 8 in the study treatment group and in the control group with a non-inferiority margin of  $\delta = 20\%$ . The null hypothesis (H0) that in the study treatment group the rate of treatment responders is less than in the control group, will be declined if the lower bound of the 97.5% one-sided CI for the two proportions difference is located to the right of the **-0.20**, with the final conclusion of non-inferiority of Levopront® versus Libexin®.

The proportion difference will be calculated using **Newcombes Hybrid Score** method (1998). See 8 [1].

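### Does the Z of 1.645 printed in SAP 2.2 put the 184 patients or the primary test in doubt?

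*SAP*

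**What the plan says.** SAP 2.2 carries a footnote marking it as "Citation from the protocol". It gives a non-inferiority formula for two independent proportions. The legend then says that the alpha quantile, written with an alpha/2 subscript, "is 1.645 for one-sided" alpha = 0.05. In the same position, Protocol 9.2 says that the quantile "is 1.96 for one-sided" alpha = 0.025.

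The SAP paragraph after the legend begins "In order to achieve power 80%, with corrected" alpha of 0.025 (one-sided) and concludes that "184 patients should be enrolled in the study at 1:1 ration (92 patients per treatment group"). Its other inputs are 70% response in both groups, a 20% margin and at most 10% early discontinuation.

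The same legend defines p1 as "success rate in the control group" and p2 as the rate in the treatment group. SAP 7.2.3 writes its hypotheses on p1 - p2 ("H1: Lower bound of the 97.5% one-sided CI" and so on, set against -20%) without defining the symbols again. The prose beneath declares Levopront non-inferior to Libexin if the "lower bound of the 97.5% one-sided CI for the two proportions difference is located to the right of the" value -0.20. Protocol 9.7.1 has the same structure.

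**The concern.** The SAP presents itself as the governing statistical document, yet this section does not match the text it cites. The printed Z does not lead to the N printed a few lines later. If 1.645 were the real design value, the trial would have been sized at one-sided 0.05 and tested at one-sided 0.025, and it would fall short of 80% power.

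The hypotheses raise a separate worry. The only definitions of p1 and p2 in either document make p1 the Libexin rate. Carried into SAP 7.2.3, they turn p1 - p2 into Libexin minus Levopront. A lower limit above -20% for that contrast is easier to reach the worse Levopront performs, which is the reverse of a non-inferiority test.

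Finally, the prose null says only that Levopront's rate is below the control rate. It leaves out the margin, although the rejection rule in the same sentence uses -0.20.

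**Working it through.** **Inputs.** p1 = p2 = 0.70, margin 0.20, Z for power 0.84, discontinuation 10%, 1:1 allocation (SAP 2.2 and Protocol 9.2). The quantile for alpha is 1.96 in the protocol legend and 1.645 in the SAP legend.

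**Formula.** n per arm = (Z_alpha + Z_beta)² × [p1(1 - p1) + p2(1 - p2)] / (p1 - p2 - margin)². With these inputs the last two factors are 0.42 / 0.04 = 10.5.

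**The stated figure first, Z = 1.96.**
- (1.96 + 0.84)² × 10.5 = 7.84 × 10.5 = 82.32 per arm
- 82.32 / 0.9 = 91.47, rounded up to 92 per arm, 184 in total. This is the plan's number.
- Rounding to 83 before inflating gives 83 / 0.9 = 92.2, so 93 per arm and 186 in total. The plan evidently inflated the unrounded value; the difference is two patients.

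**The printed SAP value, Z = 1.645.**
- (1.645 + 0.84)² × 10.5 = 6.175 × 10.5 = 64.84 per arm
- 64.84 / 0.9 = 72.04, rounded up to 73 per arm, 146 in total. That is 38 fewer than the plan states.

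**Power at the level actually tested**, Phi(0.20 / sqrt(0.42 / m) - z), where z is the one-sided quantile:

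| Evaluable per arm | one-sided 0.05 | one-sided 0.025 |
|---|---|---|
| 65 | 80.0% | 70.1% |
| 83 | 87.8% | 80.3% |

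Enrolling 92 per arm with 10% loss leaves 92 × 0.9 = 82.8 evaluable, so the stated N delivers the stated power at one-sided 0.025.

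**The subscript.** Taken literally, alpha/2 with alpha = 0.025 gives Z = 2.24 and (2.24 + 0.84)² × 10.5 = 99.6, about 100 per arm before dropout. That does not lead to 184 either. Both documents therefore use the subscript loosely; 1.96 is the alpha/2 quantile of a two-sided 0.05.

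**Direction of the contrast.**
- The sample-size legend (p1 = control) explains the symbols of one formula in another section. Since p1 = p2 at the planning values, N does not depend on the labels.
- The prose in SAP 7.2.3 names the study treatment group before the control group and ends in a conclusion about Levopront versus Libexin.
- Table shells 9.8 and 9.9 label Levopront as Test and Libexin as Control. They report Test minus Control for resolved cough, with a 97.5% interval that has a lower limit only. A footnote to the shells lets the layout vary but requires the meaning to be kept.

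The prose and the shells agree on Levopront minus Libexin.

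**The case for a change.** The strongest case for acting is that these are defects in current text, provable line by line and cheap to correct. The 1.645 cannot be excused as a description of the interim analysis at 0.05, because the legend explains the formula behind the 184, and the protocol's parallel legend has the other value. A document that claims statistical authority should not need a table shell to establish the sign of its own hypotheses. Rejecting a null of simply being below control would also assert more than a lower limit above -0.20 can support.

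The textual points stand: the legend entry is wrong, p1 - p2 is unlabelled, and the prose null omits the margin. The consequence does not. Neither document states or uses 146, and the 70.1% power belongs to a design nobody proposes. The reversed contrast requires importing a local legend across sections against both the prose rule and two table shells. The loose prose null is followed in the same sentence by the rule that decides the outcome, with its -0.20 limit.

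**Conclusion.** This is a clerical slip with some loose notation, and no change to the plan is called for. The legend's Z should read 1.96 for one-sided 0.025. The N of 184, the alpha, the margin and the one-sided 97.5% interval already agree with one another and with the protocol. The size of the slip is 146 against 184 on paper and zero patients in practice. An analyst has one coherent route through the primary analysis: the Newcombe lower limit of Levopront minus Libexin, compared with -0.20. Editing the legend or labelling the contrast would tidy the document without altering enrolment, the test or the conclusion.

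This rests on the plan's own planning values (70% in both arms, 20-point margin, 10% discontinuation), on the normal approximation in its formula, and on inflating the unrounded n. It does not address whether the margin is justified or whether the move to 0.025 is an adequate correction for the earlier look at the data; those are separate questions.

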### 2.3 STUDY OBJECTIVES

To assess the efficacy of Levopront® in comparison with Libexin® based on daytime cough resolution rate by Day 8.

The daytime cough symptoms resolution corresponds to 0 or 1 points on the "Six-point daytime and nighttime cough assessment scale".

 Zanasi et al. Levodropropizine for treating cough in adult and children: a meta-analysis of published studies *Multidisciplinary Respiratory Medicine* (2015) 10:19

 EMA CHMP Guideline on the choice of the non-inferiority margin EMEA/CPMP/EWP/2158/99, 2005

### **3. INTERIM ANALYSIS, FINAL ANALYSIS AND UNBLINDING**

No interim analysis is planned.

There is open-label study. No unblinding required.

### **4. ENDPOINTS AND COVARIATES**

#### **4.1 EFFICACY ENDPOINTS**

##### **Primary efficacy endpoint**

- To assess the efficacy of Levopront® in comparison with Libexin® based on daytime cough resolution rate by Day 8.

##### **Secondary efficacy endpoints**

- To assess the efficacy of Levopront® in comparison with Libexin® based on nighttime cough resolution rate by Day 8
- Daytime and nighttime cough symptoms resolution according to “Six-point daytime and nighttime cough assessment scale” by Day 4
- Change in severity and frequency of daytime and nighttime cough according to “Six-point daytime and nighttime cough assessment scale” on Day 4 and Day 8 from baseline on Day 1
- Cough intensity change according to the visual-analogue scale on Day 4 and Day 8 from baseline on Day 1
- Change of FEV1 on Day 8 from baseline values on Day 1

#### **4.2 SAFETY ENDPOINTS**

Rate of Adverse events (AE) and Serious Adverse Events (SAE) of the various severity according to subjective complaints, laboratory test results, physical examination, vital signs and spirometry.

### **5. ANALYSIS SETS**

#### **5.1 PER PROTOCOL POPULATION**

Per-protocol population includes all randomized patients completing treatment with the study drug, having primary efficacy analysis assessment done and considered to be compliant. Patients without serious deviations from protocol during the study will be considered compliant. The key protocol deviations will be determined before the date of database lock. PP population is the primary population for the primary endpoint (Non-inferiority) analysis

#### **5.2 INTENT-TO-TREAT POPULATION**

The population of patients is based on the initial treatment assignment and not on the treatment eventually received (ITT).

#### **5.3 SAFETY ANALYSIS SET**

All patients who received at least one dose of the study drug will be included into the safety population.

#### **5.4 PROTOCOL DEVIATIONS**

A full list of protocol deviations will be compiled and reviewed to identify major and

minor deviations prior to database lock.

## 6. HANDLING OF MISSING VALUES

### 6.1 EFFICACY PARAMETERS

Replacement of missing data is not planned for efficacy parameters.

### 6.2 SAFETY PARAMETERS

#### 6.2.1 Missing onset dates in AE

AE with missing onset date will be counted as TESS (Treatment Emergency Sign and Symptom).

In case of AE date is incomplete following rules will be used:

Day	Month	Year	Condition
Missing	Missing	In place	In case of month and year of onset > date of start study time (IC date) - TESS
Missing	Missing	In place	In case of year of onset $\geq$ year of start study time (IC date) - TESS
Missing	Missing	Missing	TESS
Missing	In place	Missing	TESS
Missing	Missing	In place	Year of onset $\geq$ year of start study time (IC date) - TESS

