6.3 Demographic Data and Medical History

To assess patient compliance to inclusion/non-inclusion criteria, patient demographic data (sex, date of birth/age, race) and full medical history, including significant acute and chronic disorders and conditions (e.g. menopause), surgical interventions and allergic reactions should be collected. Besides, patient should be asked about hospitalizations and/or surgical interventions scheduled within the study period (if applicable). All new diagnoses and conditions detected at screening (including results of laboratory and instrumental studies) should be attributed to the patient's medical history.

History of smoking is assessed by the pack/year index according to the following formula:

$$\text{Pack/year index} = \frac{\text{No. of cigarettes per day} \times \text{Smoking experience (years)}}{20}$$

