6.12 Assessment of Adverse Events (AE)

6.12.1 Definitions of AEs

Adverse Event (AE) – is any untoward medical occurrence in a clinical investigation subject administered a pharmaceutical product which does not necessarily have a causal relationship with this treatment. An adverse event (AE) can therefore be any unfavorable and unintended sign (including an abnormal laboratory finding), symptom, complaint or disorder. In this study AEs will be reported from the moment of signing Informed Consent Form (prior to administration of the first dose of the study drug) to Day 30 after the last visit of the patient or last procedure per protocol.

Adverse Drug Reaction (ADR) – any adverse event for which there is a reasonable possibility that the drug caused the adverse event. “Reasonable possibility” means there is evidence to suggest a causal relationship between the drug (at any dose) and the adverse event.

Serious Adverse Event (SAE) and/or Serious Adverse Drug Reaction (SADR) – Any adverse medical event which, irrespective of the dose of the study drug:

- results in death;
 - is life-threatening;
 - requires hospitalization (initial or prolonged);
 - results in significant, persistent or permanent impairment or disability; or
 - is a congenital anomaly or birth defect
- is an important medical event that may be not immediately life threatening or result in death or hospitalization but, based upon appropriate medical judgment, may jeopardize the patient and may require medical or surgical intervention to prevent one of the outcomes listed in the definition above.

Significant medical events that do not pose an immediate threat to life, do not result in death or hospitalization, but put patients at risk or require interventions aimed at the prevention of the above outcomes can also be included in SAE/SADR. Examples of such events may include bronchospasm of allergic genesis, convulsions, malignant neoplasms.

NOTE: Hospitalization for social reasons, visits to day patient facility, hospitalization or operation preplanned prior to patient enrollment into the study for treatment of underlying condition, are not to be considered SAEs.

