#### **7.3.1 Adverse Events**

Adverse Events will be summarized by treatment groups. Relation of AE to the therapy will be defined by AE onset date and period start date for the patient. All AEs will be coded with MEDDRA dictionary. AEs will be summarized by SOC (System Organ Class) and PT (Preferred Terms).

Adverse Events (if any) started before the first dose of the study drug(s) will be presented in the separate table.

AE frequencies will be compared between treatment groups. For such comparisons MedDRA Preferred Terms (PT) will be used. Treatment groups will be compared by set of frequencies of PT terms using permutation tests. One p-value will be provided ( $H_0$ : treatment groups are equal in set of AE frequencies).

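### SAP 6.2.1 prints one missing-date pattern three times with two conditions, and its only month-level test would fail an AE known to start in the month of consent

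*SAP*

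**What the plan says.** SAP 6.2.1 opens with a default: "AE with missing onset date will be counted as TESS (Treatment Emergency Sign and Symptom". A five-row table for incomplete dates follows.

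- Rows 1, 2 and 5 carry the same label for day, month and year: "Missing Missing In place".
- Row 1 has the condition "In case of month and year of onset > date of start study time (IC date) - TESS".
- Row 2 begins "In case of year of onset" and requires that year to be at or after the "year of start study time (IC date) - TESS". Row 5 repeats the same test.
- Row 3 (nothing known) and row 4 (only the month known) are TESS without condition.

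SAP 7.3.1 splits AEs at a different reference point: "Adverse Events (if any) started before the first dose of the study drug(s) will be presented in the separate table". That table is shell 9.32.

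On collection, Protocol 6.12.1 states: "In this study AEs will be reported from the moment of signing Informed Consent Form". Protocol 6.3 adds: "All new diagnoses and conditions detected at screening (including results of laboratory and instrumental studies) should be attributed to the patient's medical history".

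**The concern.** The table cannot be programmed as printed. One pattern has two conditions, and the case of day missing with month and year known has no row under its own label. Row 1's condition fits that case, but its strict sign sits badly with the rest of the section, where every other rule leans towards counting the AE. A date known to the month can be treated less inclusively than a date known only to the year.

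The trial's short timeline makes the sign matter. AEs are collected only from consent, and participation lasts about 10 days, so an AE in the consent month is very likely to have started on treatment. AE and SAE rates are a stated objective, and SAP 7.3.1 plans a between-group comparison of AE frequencies.

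**Working it through.** **Step 1: which row serves which pattern.** With the day missing there are four possibilities for month and year.

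| Known parts | Row that can serve it | Condition for TESS |
|---|---|---|
| Nothing | 3 | none |
| Month only | 4 | none |
| Year only | 2 and 5 | year at or after consent year |
| Month and year | 1, by its condition but not its label | month and year strictly after the consent date |

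Row 1's label says that the month is missing, yet its test needs the month. Month and year known is the only pattern left for it.

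**Step 2: apply row 1 to an AE in the consent month.** The test sets a month and year against a full date, and no imputation rule is given. There are three ways to evaluate it:

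- Compare by month: equal months are not strictly later, so the test fails.
- Set onset to the first of the month: never later than a consent date in that month, so it fails.
- Set onset to the last of the month: later than consent unless consent fell on that last day, so it nearly always passes.

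With only the year known, the same AE passes row 2 in every case.

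**Step 3: how often an onset falls in the consent month.** The plan states no figure, so none can be reproduced. Inputs:

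- Part 1 ran from 9 November 2016 to 27 April 2017 (Protocol 3.3). Consent dates are taken to 17 April 2017, assuming 10 days before the last visit: 160 dates.
- Part 2 was expected from November 2017 to February 2018 (Protocol 3.3). Consent dates are taken from 1 November to 28 February: 120 dates.
- Assumptions: consent is equally likely on each of the 280 dates, and onset is equally likely on each day of a window that starts at consent.

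Share = (consent-date and onset-day pairs in the same calendar month) / (280 × window length).

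| Window | Same month / all pairs | Share failing by month | Share passing |
|---|---|---|---|
| 8 days | 1988 / 2240 | 88.75% | 11.25% |
| 10 days | 2395 / 2800 | 85.5% | 14.5% |
| 11 days | 2585 / 3080 | 83.9% | 16.1% |
| 40 days | 4384 / 11200 | 39.1% | 60.9% |

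The 40-day window allows for spontaneous reports up to 30 days after the last visit (Protocol 6.12.3). With onset set to the last day of the month, 2791 / 2800 = 99.7% would pass in the 10-day window. A test of at or after on month and year passes 100% in every window.

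**Step 4: where the flag is used.** TESS appears in the abbreviation list and in SAP 6.2.1 only. Shells 9.33 to 9.39 are headed for the safety population with no TESS restriction. The only split by onset is shell 9.32, which is defined by first dose. Screening and randomization take place on one day (Protocol 3.1.1.1), and the first dose is taken at the site that day (3.1.1.2). Consent and first dose therefore share a calendar month, and the choice between them cannot change a month-level test.

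**The case against.** Row 1 is printed as month missing, so applying it to a known month is an inference. The label may be a drafting slip or a table broken in extraction, and the text cannot settle which. This stands. But if the inference is refused, a date known to the month has no rule of its own, which also needs correcting.

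The table does not say what an AE becomes when its condition fails, and the opening default could be read as a fallback to TESS. End-of-month imputation would also rescue nearly all these AEs. Both points stand as reasons not to assert one outcome, but the SAP adopts neither reading.

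A reader might infer that AEs will be under-counted in the safety tables. The documents do not support that: no AE shell is filtered on TESS, and an AE placed in shell 9.32 is still reported.

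The practical effect is probably small. Patients keep a daily diary (Protocol 6.10), are seen on Days 4 and 8 and telephoned on Day 10, and onset date is required for each AE (6.12.3). The rule is also the same in both arms. These points limit the size of the problem but do not make the rule correct.

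**Conclusion.** Wrong as written, minor. SAP 6.2.1 repeats one pattern with differing conditions, gives no labelled row for day missing with month and year known, and leaves the result of a failed condition undefined. On the only workable reading of row 1, and without end-of-month imputation, an AE known to start in the consent month fails, although it would be TESS if only its year were known.

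Under the uniform assumptions, about 86% of AEs with only the day missing would fail in a 10-day window, 89% in 8 days and 39% in 40 days. These are shares of a number that the documents do not give, not of all AEs. What can be shown is a risk of placement in the pre-dose table or of an undefined status. A loss of events from shells 9.33 to 9.39 cannot be shown.

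**What to change.** Before database lock, amend SAP 6.2.1 as follows:

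- Give each missing-date pattern exactly one row and delete the duplicate year-only row.
- Relabel row 1 as day missing, month and year known. Its condition becomes: TESS if month and year of onset are at or after month and year of first dose.
- Use first dose as the reference throughout, to agree with SAP 7.3.1. This is for consistency and does not change the month-level result.
- State what happens when a condition fails: count an AE as pre-dose only when the known date parts prove that it started before first dose.
- Say which AE tables, if any, use the TESS flag.

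The cost is a short text correction with no effect on design or efficacy analysis. The downside is that a few true pre-dose AEs with partial dates may be counted as treatment-emergent.
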